#### **Safety considerations**

Once a year throughout the clinical trial, a progress report is submitted to the Ethical Committee Research UZ/KU Leuven containing an overview of all serious adverse events (as defined by the Ethical Committee Research UZ/KU Leuven)[57] occurred during the reporting period and taking into account all new available safety information received during the reporting period. Adverse events will be recorded and systematically assessed during the sessions of the treatment. If adverse events are reported, these will be documented in a separate document by the therapists who provide the treatment and reported to the Ethical Committee Research UZ/KU Leuven, both directly after the report and annually in a summary. The following minimum information is recorded for each adverse event: 1) description, 2) start and stop, 3) severity and seriousness, 4) causality assessment to the study treatment, 5) outcome.

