### **Intervention and comparison**

SIESTA is based on a CBT sleep intervention for typically developing adolescents and a CBT intervention focused on motivational planning for adolescents with ADHD, both developed by (amongst others) the project applicants.[36,37] The training follows a structured workbook for the adolescent which can be used during sessions and at home.[24] The instructions for the therapist are described in a therapist manual.[25] SIESTA consists of seven individual sessions with the adolescents, and two parental sessions. An overview of the content of the sessions can be found in Table 2. This RCT uses as control condition TAU for ADHD symptomatology. In Flanders TAU for ADHD primarily consists of medication with stimulants.

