
When the adolescent meets inclusion criteria, the adolescent has to fill out the pretest questionnaires in Qualtrics. Parent(s)/guardian(s) of the adolescent are also asked to answer questionnaires in Qualtrics; also, they are asked to mail the link of the questionnaire (CPS) in Qualtrics to the teachers of the adolescent for their evaluation of the adolescent. Moreover the teacher will be asked how many lesson times per week he/she has contact with the participant. The names of the teachers will not be known by the researchers.

After the pretest is conducted, appointments for the treatment are made. However, participants are informed that those appointments can either happen as planned or that the treatment will take place 6 months later, due to the condition their child was assigned to. To avoid the possibility of a systematic bias in the assignment of participants to both groups (SIESTA treatment and treatment as usual (TAU) versus TAU only), randomization happens. We will use a stratified permuted block randomization based on medication use (yes/no) in blocks of 2 participants whereby an independent researcher performs the randomization. After the last treatment session, both the adolescent who followed the treatment and the paired adolescent from the TAU-group, are contacted by the researchers and provided with the actigraphs. The daily sleep logs are again filled out in Qualtrics. Within one week after the last treatment session a posttest session is planned in which the adolescent and parent(s)/guardian(s) are asked to fill out the questionnaires in Qualtrics. Filling out the questionnaires should not take longer than 1 hour for any informant. The actigraphs will again be picked up by a researcher or the courier service. The same procedure is applied during the follow-up measure after 3 months, including the actigraph/daily logs and the questionnaires. After follow-up, the treatment is provided to the adolescent in the TAU-group from that block.

In case of serious adverse events or a crisis situation, e.g. suicidality, during any phase of the study, (previously involved) clinicians will be contacted by the researchers. Also, if necessary at any time of the study, additional psychological aid can be given.

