### **Safety**

Recording of adverse events: The participant will be asked to report any adverse event related to the study-specific intervention to the study team. These reported events will be documented by the Investigator in the source documents.

The following minimum information should be recorded for each AR:

- AE description
- start and stop date of the AR
- severity
- seriousness
- causality assessment to the study interventions
- outcome

Reporting to the Ethics Committee

The sponsor will assess whether any relevant safety information that becomes available during the study should be reported ad hoc to the EC.

The sponsor has the obligation to, once a year throughout the clinical trial (or on request), submit a progress report to the EC containing an overview of all SARs occurred during the reporting period and taking into account all new available safety information received during the reporting period.

During the first two sessions of the intervention, participants can freely report any adverse event related to the study-specific intervention to their therapist. From the third session on the following question will be posed: "Has anything happened last week that was a danger to you? Like suicidal thoughts, risk-seeking for example bingedrinking, or anything like that.". We argue that posing this question best starts during the third session as during the first two sessions the main focus is on forming a relationship and building trust. However, asking this type of question is not a risk factor to elicit suicidal thoughts or behavior even in at-risk adolescents. Research shows that talking about suicide and idealization, reduces suicide and improves mental health (e.g. Dazzi et al., 2014).

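### Adverse events are asked about on a schedule only in SIESTA sessions, so event counts by arm could not be interpreted

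*Combined protocol and SAP*

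**What the plan says.** Safety considerations places the process inside therapy: "Adverse events will be recorded and systematically assessed during the sessions of the treatment". Events that come to light are recorded by the treating staff: "these will be documented in a separate document by the therapists who provide the treatment".

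The Safety section describes how this works. At first the adolescent may volunteer events: "During the first two sessions of the intervention, participants can freely report any adverse event related to the study-specific intervention to their therapist". After that, "From the third session on the following question will be posed". The question concerns danger to the adolescent in the preceding week, with suicidal thoughts and risk-seeking as examples.

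Two routes are not limited to one arm. In the Safety section: "The participant will be asked to report any adverse event related to the study-specific intervention to the study team". In Ethics & procedure, the researchers contact clinicians "In case of serious adverse events or a crisis situation, e.g. suicidality, during any phase of the study".

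On exposure to sessions, Intervention and comparison says "SIESTA consists of seven individual sessions with the adolescents, and two parental sessions". For controls, Ethics & procedure says "After follow-up, the treatment is provided to the adolescent in the TAU-group from that block", and the note to Figure 1 places that later treatment outside the study protocol.

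**The concern.** A harm that one arm is asked about repeatedly and the other must volunteer will be recorded more often in the first arm, even if it is equally common in both. Here the arm that is asked is the one receiving the new treatment. An excess of recorded events in SIESTA could be produced by the asking alone, and a real protective effect could be hidden.

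The question covers suicidal thoughts and risk-taking in 13- to 17-year-olds. The Dissemination plan foresees wide implementation if SIESTA proves effective, so readers will want to know what happened in each arm. As planned, the trial could not tell them, although it is randomized and already contacts both arms at post-test and follow-up.

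**Working it through.** The documents give no adverse-event rate, power statement or comparison, so there is no planned figure to reproduce. The check is a count of scheduled enquiries, followed by an illustration.

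**1. Scheduled prompts per adolescent**

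- SIESTA: seven adolescent sessions, with the question put from session 3 on. 7 − 2 = 5 prompts at full attendance. With 46 per arm (Sample size estimates), 46 × 5 = 230 prompts.
- TAU: no sessions before the last follow-up, so 0 prompts.

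**2. Other scheduled contacts**

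Outcome measures, the section on where treatment is provided, and Ethics & procedure describe the assessments. None lists an adverse-event item at pre-test, post-test or follow-up. After session 7, SIESTA adolescents also have no scheduled question through the roughly three months to follow-up. By contrast, Statistical analysis does plan an explicit check of medication use at post-test and follow-up, so a check of this kind is feasible at those visits.

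**3. What the routes open to both arms can capture**

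- The general request to report is limited to events related to the study-specific intervention. TAU adolescents have not received it, so an event of theirs would rarely qualify.
- The serious-event and crisis route starts once an event is known. It contains no means of finding one.

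**4. What unequal detection does to counts (illustration)**

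Let p be the true risk, s1 the detection probability in SIESTA and s0 that in TAU. Expected recorded cases are 46 × p × s1 and 46 × p × s0. With equal true risk, the recorded ratio is s1/s0 whatever the value of p. All values of p, s1 and s0 below are assumptions; none comes from the documents.

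| True risk, both arms | SIESTA, s1 = 0.9 | TAU, s0 = 0.5 | TAU, s0 = 0.3 | TAU, s0 = 0.1 |
|---|---|---|---|---|
| 10% | 4.1 | 2.3 | 1.4 | 0.5 |
| 20% | 8.3 | 4.6 | 2.8 | 0.9 |
| 30% | 12.4 | 6.9 | 4.1 | 1.4 |
| Recorded ratio | – | 0.9/0.5 = 1.8 | 0.9/0.3 = 3.0 | 0.9/0.1 = 9.0 |

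For example, at 20%: 46 × 0.20 × 0.9 = 8.3 and 46 × 0.20 × 0.5 = 4.6.

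More generally, the recorded ratio is the true ratio multiplied by s1/s0. With s1/s0 = 1.8, a true risk ratio of 1/1.8 = 0.56 in favour of SIESTA would appear as no difference.

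**5. With the same question in both arms**

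If detection is 0.9 in each arm, a 20% risk gives 8.3 expected cases per arm and a ratio of 1.0.

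**The case against.** The strongest reply is that the plan never sets out to compare harms. Statistical analysis specifies mixed models for the outcomes only, adverse events are neither a primary nor a secondary outcome, and the stated use of the records is documentation and reporting to the ethics committee. This is correct. A reader might infer that a planned harms comparison is biased; the documents contain no such comparison. What remains is that any counts shown by arm would be uninterpretable.

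A reader might also infer that TAU adolescents are never asked anything. The Safety section's general request is not restricted by arm, so the supportable statement is that they are not asked systematically.

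A third tempting reading is that the crisis commitment in Ethics & procedure cannot be met for TAU. That sentence promises a response to known events, not screening, and it can be honoured for any event that reaches the researchers. The fair criticism is that nothing scheduled brings such events to light. Table 1 excludes depressive disorder with suicide risk and active suicidality at entry, which lowers the risk without removing it.

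Finally, depressive symptoms (CDI-2), anxiety (SCARED-R) and oppositional symptoms (DBDRS) are secondary outcomes with no restriction by arm. Worsening on these scales can be compared without this ascertainment problem and can support the harms picture. They are symptom scales and do not replace adverse-event enquiry.

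**Conclusion.** The point holds as a matter of ascertainment. Following the plan as written gives up to five scheduled enquiries per SIESTA adolescent and none per TAU adolescent up to the 3-month follow-up. Neither arm has a scheduled enquiry after session 7. This rests on the documents alone, apart from the assumption of full attendance behind the figure of five.

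The consequence is conditional: if events are reported by arm, equal true risk will show as an apparent SIESTA excess whenever detection is lower in TAU. The size cannot be derived from the documents. The range of 1.8 to 9.0 is simply the ratio of assumed detection rates and should not be read as an estimate. The efficacy analyses are not affected. This is a change that should be made because it is cheap and improves both safety ascertainment and the fairness of any later account of harms.

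**What to change.** - Add one identical adverse-event item to the existing Qualtrics questionnaires of both arms at post-test and follow-up. It should not depend on relation to the intervention. Its recall window should cover the whole interval since the previous assessment; reusing the session question's one-week window would leave most of the three months to follow-up unasked.
- Base any comparison of arms only on events collected this way. Report events elicited in sessions separately, as descriptive for SIESTA.
- If data collection is too advanced, state that adverse-event data are descriptive for SIESTA only and that the arms are not to be compared.
- Separately, reconcile Safety with Safety considerations. The first has the investigator document events in source documents, the sponsor judge whether to report ad hoc, and an annual overview of SARs. The second has therapists use a separate document, report directly to the committee as well as annually, and give an annual overview of serious adverse events.

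The cost is a short amendment, a slightly longer questionnaire at two existing assessments, and a procedure for prompt review of responses by the study team, since the item may elicit reports of suicidal thoughts online. Two items will not give early warning of a crisis arising between assessments; they make ascertainment equal but do not provide continuous monitoring.

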#### **Dissemination plan**

Implementation is a major part of this project. To this end an advisory board is involved from the start of the project; they meet twice yearly in the first and last year, and yearly in the second and third year of the project and on demand. This board consists of important societal representatives of mental health care in Flanders i.e. the advisory board consists of representatives of private practices, the Flemish Behavior Therapy Association, the ADHD reference network Flanders, the Specialized sleep center UZ Leuven, the Patient organization ADHD ZitStil, Sig vzw (educational organization rehabilitation centers), the Belgian Association for Sleep research and Sleep medicine, and the European ADHD Guidelines group. Also, the project partners are involved in governmental organizations relating to mental health care policy (e.g. members of the Hoge Gezondheidsraad ADHD; expert advisory board to the minister of health in Belgium; members of the European ADHD Guidelines Group). Both the project applicants and the advisory board will join forces across four lines of (mental) health care for optimal implementation when SIESTA is proven effective; line 1) governmental organizations and mental health care policy makers/non-discriminatory transfer to the EU, line 2) mental health care organizations, specialized sleep centers, and a network of sleep experts in Flanders, line 3) clinicians and other professionals working with adolescents with ADHD and/or individuals with sleep problems, and line 4) patient organizations, adolescents with ADHD and their parents. These combined efforts will lead to an optimal implementation of the following products and knowledge acquired by this project if proved effective: a workbook and therapist manual of SIESTA, a training module for clinicians wanting to provide SIESTA, and a website containing all information and training materials regarding SIESTA for adolescents, parents, clinicians, mental health organizations and governmental organizations. Additionally, results of the study will be communicated to other researchers via publications in academic journals and presentations at conferences.

#### **Funding statement**

This work was supported by Research Foundation Flanders (FWO – Fonds Wetenschappelijk Onderzoek), grant number T002319N.

The funding source had no role in the design of this study and will not have any role during its execution, analyses, interpretation of the data, or decision to submit results.

